1.1. Intratympanic formulation of gacyclidine (OTO-313)

Intratympanic administration permits deposition of drugs over the round window membrane. This enables access to the inner ear for more localized delivery to the cochlea and less systemic drug exposure (Bird et al. 2007). Gacyclidine, the active agent in OTO-313, is a noncompetitive NMDA-receptor antagonist that is considered to have greater potency, faster on-rate, and slower off-receptor rate than other NMDA-receptor antagonists (Mitha and Maynard 2001; Piu et al 2018). Gacyclidine was originally formulated as OTO-311, [REDACTED] to provide sustained exposure of

gacyclidine to cochlear tissues following a single intratympanic administration. Additional preclinical studies showed that gacyclidine formulated [REDACTED] (OTO-313) provided greater and longer lasting inner ear exposures of gacyclidine compared to OTO-311 when injected intratympanically.

1.2. Clinical studies with OTO-313

Gacyclidine was originally studied using intravenous administration in clinical studies in spinal cord and brain trauma patients and no concerning safety issues were identified. Gacyclidine has also been administered to the otic compartment in an open label study in patients with chronic tinnitus. The drug was generally safe and well-tolerated and reduced subjective tinnitus ratings in 4 of the 6 subjects evaluated ([Wenzel, et al. 2010](#)). In a completed Phase 1 study in healthy subjects (Study 311-201501), OTO-311 (the earlier formulation of gacyclidine), placebo or sham was administered as a single intratympanic injection. All OTO-311 dose levels tested (0.15 mg, 0.3 mg, and 0.6 mg) were well-tolerated and no safety concerns were identified.

Study 313-201901 was a randomized, double-blind, placebo-controlled Phase 1/2 study which evaluated the safety and exploratory efficacy of a single intratympanic administration of OTO-313 in subjects with subjective tinnitus. An initial safety and plasma PK cohort of 8 subjects dosed with 0.11 mg OTO-313 or placebo (3:1) demonstrated that this dose level was well-tolerated with no safety concerns. An exploratory efficacy cohort of 35 subjects with unilateral tinnitus of moderate to severe intensity (score of ≥ 25 on the Tinnitus Functional Index [TFI]) and a duration of tinnitus of 1 to 6 months received a single intratympanic injection of 0.32 mg OTO-313 or placebo (1:1). 0.32 mg OTO-313 was well-tolerated with a lower incidence of adverse events than placebo.

In the exploratory efficacy cohort, the mean TFI reduction from baseline trended in favor of OTO-313 at each timepoint (Day 15: -9.3 points OTO-313 vs -4.1 points Placebo; Day 29: -9.4 points OTO-313 vs -6.6 points Placebo; Day 57: -12.9 points OTO-313 vs -4.3 points Placebo). A clinically meaningful, 13-point improvement on the TFI was observed in 43% (6/14) of OTO-313 subjects at both Day 29 (Week 4) and Day 57 (Week 8) versus 13% (2/16) of Placebo subjects (*ad hoc* 1-sided p-value < 0.05). The higher responder rate for OTO-313 versus Placebo was maintained for all TFI improvement levels of 15, 20, 25 and 30 points. Treatment with OTO-313 also led to reduction in the daily ratings of tinnitus loudness and annoyance, as well as improved PGIC scores. Among responders, strong correlation was observed between the various endpoints in favor of OTO-313. As anticipated, plasma concentrations of gacyclidine were below the limit of assay quantitation (≤ 0.1 ng/mL) confirming limited systemic exposure. These results suggest that a single intratympanic injection of 0.32 mg OTO-313 was well-tolerated and exhibited preliminary efficacy in subjects with unilateral tinnitus.

1.3. Rationale for current study

The purpose of this Phase 2 study, Study OTO-313-201, is to investigate the efficacy and safety of 0.32 mg OTO-313 administered by intratympanic injection in subjects with unilateral tinnitus.

The 0.32 mg OTO-313 dose level is expected to be safe and well-tolerated, based on Study 313-201901 in subjects with unilateral tinnitus. In addition, preclinical data suggest that this dose level of OTO-313 will produce sufficient inner ear exposures of gacyclidine in humans. The

lipid formulation of OTO-313 is expected to maintain sustained exposures to the cochlea over time (at least 7 to 14 days in preclinical testing). Taken together, the preclinical and clinical data support the evaluation of 0.32 mg OTO-313 in this Phase 2 study in subjects with unilateral tinnitus.

The preclinical and clinical data obtained to date are described in more detail in the Investigator's Brochure.

2. OBJECTIVES

2.1. Primary objective

- To determine the efficacy of OTO-313 in subjects with unilateral tinnitus by comparing the proportion of subjects achieving response using the TFI relative to placebo.

2.2. Secondary objectives

- To determine the effect of OTO-313 across additional secondary measures of efficacy (tinnitus loudness and annoyance NRS, PGIC, SF-12) relative to placebo.
- To determine the safety and tolerability of OTO-313 in subjects with unilateral tinnitus.

3. OVERVIEW OF STUDY DESIGN

This study will be conducted at approximately 55 sites globally.

The duration for each subject will be approximately 18-22 weeks, including an up-to 4-week Screening period, a 2-week Lead-in assessment period, and a 16-week Follow-up period.

[figure not shown]
After signing informed consent, subjects will complete the TFI at the Screening visit. Subjects must have an overall score of ≥ 32 on the TFI at both Screening and Baseline. After Screening, potential subjects will begin a 2-week Lead-in assessment period. During this time, subjects will enter daily tinnitus annoyance and tinnitus loudness severity into a diary using the appropriate Numeric Rating Scales (NRS) for each symptom. Subjects must have completed the tinnitus diary on at least 5 of the last 7 days of the 14-day Lead-in period for eligibility. The additional +5 days of the Lead-in period will not be used for eligibility.

At the Baseline (Day 1) visit, approximately 140 eligible subjects will be randomized to OTO-313 or placebo using a 1:1 allocation ratio. Randomization is stratified by study site, duration of tinnitus (≥ 2 to ≤ 6 months and >6 to ≤ 12 months since onset) and by the average of the TFI score at Screening and Baseline (≥ 32 to ≤ 53 points, ≥ 54 to ≤ 100 points).

After a single intratympanic injection with 0.32 mg OTO-313 or placebo to the affected (study) ear on Day 1, subjects will continue to record their tinnitus annoyance and tinnitus loudness on a daily basis using the diary during the 16-week Follow-up period. Subjects will complete the TFI at study visits at Week 4, Week 8, Week 12, and Week 16. Additional efficacy and/or safety assessments will also be completed at Baseline (Day 1), Week 4, Week 8, Week 12, and Week

16 or upon early termination from the study. An independent Safety Review Committee will review accumulated individual subject safety data to ensure appropriate safety and tolerability of OTO-313 or placebo.

Figure 1. Study Design Schematic

4. STUDY POPULATION

4.1. General Considerations

Approximately 140 subjects will be enrolled at approximately 55 sites globally. Subjects will be eligible if they meet all of the following inclusion criteria and none of the exclusion criteria.

4.2. Inclusion Criteria

To be eligible for this study, each of the following criteria must be satisfied with a “YES” answer (unless not applicable):

1. Subject is a male or female aged 18 to 75 years, inclusive.
2. Subject has subjective unilateral tinnitus and is consistently aware of their tinnitus throughout much of the waking day.
3. Subject’s tinnitus is likely of cochlear origin, e.g., associated with sensorineural hearing loss; acute hearing loss from noise trauma, barotrauma, or traumatic cochlear injury (acute acoustic trauma, blast trauma, middle ear surgery, inner ear barotrauma); age-related hearing loss; resolved otitis media; ototoxic drug exposure.

4. Subject's self-reported duration of tinnitus is between 2 months and 12 months (≥ 60 to ≤ 365 days) prior to signing informed consent.
5. Subject has an overall score of ≥ 32 on the TFI at both Screening and Baseline visits.
6. Subject has audiometrically-defined normal hearing or up to moderately severe hearing impairment in the affected ear (study ear) as characterized by pure tone average of ≤ 70 dB at 1000, 2000, and 4000 Hz at Screening.
7. Subject is able to use the diary to complete their daily tinnitus ratings and has completed at least 5 of the last 7 days of diary entries during the 14-day Lead-in period.
8. Female subjects of childbearing potential [i.e., not surgically sterile and/or not post-menopausal (≥ 12 months since last menstrual period without an alternative medical cause)] must have a negative urine pregnancy test at Baseline. Women of childbearing potential who are not abstinent from sex with male partners must use highly effective methods of contraception for the duration of the study including: established use of oral, injected, or implanted hormonal methods of contraception; or placement of an intrauterine device or intrauterine system. Female subjects of childbearing potential must also refrain from egg donation or retrieval for the duration of the study.
9. Male subjects (unless surgically sterile) who are not abstinent from sex with female partners of childbearing potential must agree to use an effective contraceptive method (as detailed for Inclusion Criteria 8) for the duration of the study. Male subjects must refrain from sperm donation for the duration of the study.

Note: Abstinence (male or female subjects) is acceptable if this is the usual lifestyle and preferred contraception for the subject. Periodic abstinence, the rhythm method, and the withdrawal method are not acceptable.

10. Subject is willing to comply with the protocol and attend all study visits.
11. Subject is able to provide written informed consent, including agreement to privacy language compliant with country and/or local requirements, after the scope and nature of the investigation have been explained, and before the initiation of any study-related procedures.

4.3. Exclusion Criteria

To be eligible for this study, each of the following criteria must be satisfied with a “NO” answer: (unless not applicable):

1. Subject has pulsatile tinnitus, temporomandibular joint disease associated with tinnitus perception, tinnitus resulting from traumatic head or neck injury, or tinnitus resulting from a tumor or stroke.
2. Subject has active middle ear disease (including but not limited to: chronic otitis media, acute otitis media, middle ear effusions, middle ear atelectasis, otosclerosis, Eustachian tube dysfunction, or cholesteatoma), Meniere’s disease as outlined by the American Academy of Otolaryngology-Head and Neck Surgery Equilibrium Committee in 2015 ([Goebel 2016](#)), concurrent vestibular pathology, or vestibular schwannoma.
3. Subject has recently (< 1 month of Screening) initiated new treatment for tinnitus (e.g., noise or sound generators, hearing aids, behavioral therapy, non-conventional therapy, medications or over-the-counter supplements, transcranial magnetic stimulation); only stable tinnitus treatments (i.e., initiated at least 1 month prior to Screening) are allowed

during the study and no new treatments should be introduced during the course of the Study.

4. Subject is not able to accurately localize, identify, and report their tinnitus per Investigator's opinion.
5. Subject has an abnormality of the tympanic membrane in the affected (study) ear that would increase the risk associated with intratympanic injection, including but not limited to monomeric tympanic membrane.
6. Subject has evidence of perforation or lack of closure of the tympanic membrane, or a myringotomy tube in affected ear at Screening or Baseline visits.
7. Subject is receiving any ongoing therapy known as potentially tinnitus-inducing (e.g., aminoglycosides, ototoxic chemotherapeutic drugs, high doses of intravenous loop diuretics, quinine, high doses of aspirin or other nonsteroidal anti-inflammatory drugs). Usage of low doses of aspirin (e.g., daily doses of 81 mg) or low doses of other non-steroidal anti-inflammatory drugs for intermittent pain relief may be permitted at the Investigator's discretion (see [Section 7.1](#)).
8. Subject answered "Yes" to Question 4 or 5 regarding active suicidal ideation on the C-SSRS administered at Screening or Baseline visits. In addition, subjects deemed by the Investigator to be at significant risk of suicidal behavior should be excluded.
9. Subject has severe or untreated depression or anxiety that, in the Investigator's opinion, would likely reduce the safety of study participation. Antidepressant and anti-anxiety medications are allowed only if administered at stable doses and frequency for ≥ 1 month prior to Screening with the expectation that the stable daily dose will continue for the duration of the study.
10. Subject is pregnant, lactating, or undergoing fertility treatment.
11. Subject has a history of serious substance abuse (e.g., cocaine, heroin) within 6 months prior to Screening.
12. Subject has received or is receiving concomitant treatment with any other NMDA receptor antagonist (e.g., memantine, dextromethorphan) within 30 days prior to the Baseline visit. Note, occasional use of dextromethorphan for cough suppression is allowed except between 7 days prior to Baseline and 7 days after injection of the investigational product.
13. Subject has a history of any use of intratympanic gentamicin in the affected ear.
14. Subject has received systemic or intratympanic steroids (including dexamethasone) within 6 weeks prior to the Screening visit.
15. Subject has previously participated in a clinical study with OTO-313 or OTO-311.
16. Subject has used moderate or strong inducers of CYP2B6 (e.g., carbamazepine, efavirenz, rifampin, or ritonavir) within 30 days prior to Baseline visit.
17. Subject has used an investigational drug or device within 30 days prior to Screening.
18. Subject has other clinically significant illness, medical condition or medical history at Screening or Baseline that, in the Investigator's opinion, would likely reduce the safety of study participation or compliance with study procedures.

5. RANDOMIZATION AND BLINDING

5.1. Overview

Approximately 140 eligible subjects will be assigned randomly to 0.32 mg OTO-313 or placebo using a 1:1 allocation ratio, based on a computer-generated randomization schedule.

- 0.32 mg OTO-313; single (0.2 mL volume) intratympanic injection to the affected (study) ear
- Placebo (vehicle); single (0.2 mL volume) intratympanic injection to the affected (study) ear

OTO-313 and placebo solutions are identical in appearance.

5.2. Enrollment Procedures

5.2.1. Assignment of Subject Identification Numbers

At the Screening visit (Visit 1), subjects who have signed the informed consent will be assigned a sequential subject identification number by the site. Once assigned, the subject identification number will not be re-assigned and should not be changed. This number will be used to identify the subject throughout the study, including the Screening and Lead-in periods. Any subject that is re-screened will be assigned a new subject identification number. Subjects will be considered enrolled into the study once they complete the informed consent process.

The subject identification number will consist of 9 digits separated by 2 hyphens (e.g., 201-XXX-YYY). The first 3 digits are the study number (201) followed by a hyphen. The second 3 digits are the site number followed by a hyphen. The final 3 digits are the subject number.

5.2.2. Treatment Assignment

After a subject has met all prerequisites for randomization on Day 1 (Baseline/Visit 2), study sites will execute each randomization via the Interactive Response Technology (IRT) randomization system. All study site personnel are blinded to treatment assignment. Study sites will receive a randomization notification indicating the kit number (packaged investigational product), and the date and time of randomization for each subject. Once assigned, kit numbers cannot be re-assigned.

Study sites will provide the information contained in the IRT randomization notification to the person responsible for preparation of the syringe containing investigational product (OTO-313 or placebo). The unique kit number provided by IRT will correspond to a kit of packaged investigational product labeled with the identical kit number. The syringe will be prepared from the contents of the investigational product package corresponding to the IRT kit number according to the instructions in the study Pharmacy Manual. The subject identification number and kit number both must be recorded in the subject's record.

5.2.3. Randomization Algorithm

Subjects will be randomized in a 1:1 ratio (OTO-313:placebo) of treatment groups using a permuted block randomization algorithm. Randomization is stratified by study site, duration of

tinnitus (≥ 2 to ≤ 6 months and > 6 to ≤ 12 months since onset) and by the average of the TFI score at Screening and Baseline (≥ 32 to ≤ 53 points, ≥ 54 to ≤ 100 points).

The randomization process will be deployed via IRT which is accessible 24 hours a day to authorized users. The subject's randomization number will determine the randomized treatment assignment. Investigational product kits will be labeled with a unique kit number using a separate and independent randomization algorithm. Numbered kits will be dispensed based on the treatment assignment.

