5.3. Blinding

The study will be double-blinded. Each treatment syringe will be prepared according to the detailed instructions in the Pharmacy Manual.

In case of emergency, the blind should be broken for site personnel only if knowing the subject's treatment allocation would facilitate specific medical treatment. In all cases, the Investigator should consult with the medical monitor prior to unblinding, and if not possible as soon as it is practical after unblinding has occurred and treatment initiated.

If the blind is broken, the subject will continue to be followed and evaluated per-protocol. The date, time, and reason for the unblinding must be documented on the appropriate page of the eCRF.

The randomization schedule or blocking factor(s) will not be revealed to study subjects, Investigators, clinical staff, site managers or the Sponsor until all subjects have completed the study and the database has been finalized by the Sponsor.

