11.5. Sample Size

The primary endpoint is the percentage of responders, where response is defined as achieving at least a 13-point reduction from baseline in the TFI total score at both Weeks 4 and 8. It was observed from the previous study (Study 313-201901) that the response rate for OTO-313 (0.32 mg) was 43% and 13% for placebo. Based on these results, the assumed rate of response for OTO-313 is 43% and 18% for placebo, which is the 13% observed response rate in previous study plus 5% inflation for potential placebo response.

Assuming a 2-sided test and level of significance of 0.05, 60 subjects in the placebo arm and 60 subjects in each of the OTO-313 arms will provide approximately 85% power to detect a treatment difference in favor of OTO-313. It is also assumed that an observed discontinuation rate of 15% will be observed, hence the total sample size is planned to be 140 subjects, 70 subjects per arm. These sample size calculations were conducted using EASTv6.5 software with a test for a difference in proportions between two groups.

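### Crossing about 55 sites with four duration-by-TFI strata gives about 220 permuted-block cells for about 140 subjects, so the stratification loses much of its trial-wide balance

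*Combined protocol and SAP*

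**What the plan says.** Section 5.2.3 sets equal allocation to the two arms and names the method, "using a permuted block randomization algorithm. Randomization is stratified by study site, duration of" (the sentence then goes on to the other two factors). Duration has two bands: "≥ 2 to ≤ 6 months and > 6 to ≤ 12 months since onset". The TFI factor, taken as the mean of two pre-dose visits, also has two: "≥ 32 to ≤ 53 points, ≥ 54 to ≤ 100 points". The synopsis (Study Design and Methods) and Section 3 repeat the three stratifiers. Section 4.1 gives the scale: "Approximately 140 subjects will be enrolled at approximately 55 sites globally".

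The block size is withheld. Section 5.3 states that "The randomization schedule or blocking factor(s) will not be revealed to study subjects, Investigators, clinical staff" and others until the end of the study. The documents describe no pooling of sites, minimum or cap per site, minimization, or constraint on overall balance. They give no reason for stratifying by site.

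**The concern.** A permuted block guarantees equal arms only when it is filled. A block that receives one subject acts as a coin toss, and a block that is partly filled gives partial control. When the cells outnumber the subjects, most blocks are left open at the end of recruitment and their leftover imbalances add up across cells. Duration and TFI are then balanced only inside each site's small cells, with nothing to balance them across the trial.

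At stake is how evenly the 70 subjects per arm of Section 11.5 are delivered, and how comparable the arms are on two factors that the protocol uses both to stratify and to adjust the primary test. A visible imbalance on either factor would have to be explained when a Phase 2 responder result is read.

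**Working it through.** **Inputs.** About 55 sites and 140 subjects (Section 4.1). Two duration bands, two TFI bands and 1:1 permuted blocks (Section 5.2.3). Response rates and alpha from Section 11.5: "the assumed rate of response for OTO-313 is 43% and 18% for placebo", and "Assuming a 2-sided test and level of significance of 0.05". Block size (2, 4 or 6) and recruitment pattern are assumptions: either equal sites or uneven sites with gamma weights (shape 1 or 0.5). The four duration-by-TFI combinations are taken as equally common.

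**The plan's own power figure.** With n = 60 per arm, p1 = 0.43, p2 = 0.18 and pooled rate 0.305:

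z = [0.25 × √60 − 1.96 × √(2 × 0.305 × 0.695)] / √(0.43 × 0.57 + 0.18 × 0.82) = (1.936 − 1.276) / 0.627 = 1.05

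This gives 85.4% power, so the stated 85% is reproduced. After 15% dropout, 140 × 0.85 = 119, which agrees with 120 evaluable to within one subject.

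**Cell count.** 55 × 2 × 2 = 220 cells; 140/220 = 0.64 subjects per cell; 140/55 = 2.5 per site.

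**Occupancy, equal sites.** The count in a cell is Binomial(140, 1/220). About 104 cells are occupied: 74.3 hold one subject, 23.6 hold two, 5.0 hold three and 0.9 hold four or more. So 74.3/140 = 53% of subjects are alone in their cell. With uneven sites there are 41 to 53 single-subject cells, or 29% to 38% of subjects.

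**Started blocks that fill.**

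| Block size | Equal sites | Uneven sites |
|---|---|---|
| 2 | 28% | 39–46% |
| 4 | 0.8% | 6–11% |
| 6 | 0.0% | 0.8% |

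**Arm difference by hand, equal sites.** Let r subjects sit in an open block of size b. The squared arm difference of that block has expectation r(b − r)/(b − 1). Summing over the expected cells:

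- b = 2: 74.3 + 5.0 + 0.1 = 79.4, SD 8.9.
- b = 4: 74.3 + 23.6 × 4/3 + 5.0 + 0.1 = 110.8, SD 10.5.
- b = 6: 74.3 + 23.6 × 1.6 + 5.0 × 1.8 + 0.8 × 1.6 + 0.1 ≈ 122.4, SD 11.1.
- Simple randomization: 140, SD 11.8.

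Multiplying each SD by √(2/π) = 0.798 gives mean absolute differences of about 7.1, 8.4, 8.8 and 9.4. Simulation of the same scenarios gives 7.0, 8.2 and 8.7 for the three block sizes.

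**Simulation over all assumed block sizes and recruitment patterns.**

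| | Plan | Simple randomization | Central blocks, four strata |
|---|---|---|---|
| Mean arm difference | about 6–9 | about 9.4 | about 1.0–1.6 |
| Arm difference 10 or more | 21–40% | about 45% | 0% |
| Arm difference 14 or more (63:77 or worse) | 8–23% | 27% | about 0% |
| At least one duration-by-TFI stratum off by 8 or more | 14–55% | 60–62% | 0% |
| Mean difference within one duration or TFI level | 4.1–6.2 | 6.6 | 0.7–1.2 |

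Repeated runs differ by about one percentage point.

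**Cost in power.** A 63:77 split leaves about 54:66 evaluable. Then 54 × 66/120 = 29.7, against 60 × 60/120 = 30, and power is 85.3% instead of 85.4%. To include imbalance within strata, take a Mantel-Haenszel analysis over the four duration-by-TFI strata. With blocks of 4 and equal sites it keeps on average 97.7% of the maximum weight, so n = 60 × 0.977 = 58.6 and power is 84.6%. At the 5th percentile the weight is 94.5%, n = 56.7, and power is 83.3%. With blocks of 2 and strongly uneven sites the average weight is 98.9%, or about 85.0% power.

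**The case against.** The case for leaving the scheme alone is substantial, and most of it stands.

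- The scheme is a valid randomization, and its chance imbalance introduces no bias.
- Both descriptions of the primary test, in the synopsis and in Section 11.4.2.1, control for duration and baseline TFI. A chance imbalance on those factors is therefore largely handled in the analysis.
- The power at stake is small, as shown above, and the protocol speaks only of approximately 140 subjects.
- Blocks of 2 with uneven sites keep a good part of the balance. In that setting a stratum is off by 8 or more in 13% to 20% of trials, against about 61% under simple randomization.

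A reader might infer that the allocation is no better than simple randomization. That fits blocks of 4 to 6 with equal sites fairly well, but not the whole range. The documents give neither the block size nor the recruitment pattern that would settle it.

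A reader might also infer that duration and TFI were chosen because they predict response. No section gives a reason for choosing any stratifier or reports such a relation. The point rests only on the protocol's own use of them as stratifiers and adjustment factors.

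What the objection does not remove is the gap to a central scheme. In every scenario tried, blocks within the four strata bring the mean arm difference down to about 1.0 to 1.6.

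**Conclusion.** The point holds as one of efficiency and balance. The 220 cells follow directly from the documents. Most blocks stay incomplete for every block size and recruitment pattern tried, and much of the trial-wide balance is lost. The exact size within the tabulated ranges depends on the assumed block size, site recruitment and equal strata.

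Two stronger conclusions are tempting and not supported. One is that the trial is exposed to bias or an inflated type I error; nothing in the scheme produces either. The other is that the planned 85% power is materially at risk from the allocation. The average loss is about 1 percentage point or less when the analysis stratifies on duration and TFI, and about 2 points at the 5th percentile of the blocks-of-4 scenario. Whether Section 11.4.2.1 should also control for site is a separate question about the analysis, and it lends no weight here.

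The change is worth making because it costs little and cannot be made once subjects have been randomized.

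**What to change.** Before the first randomization, remove study site as a randomization stratum. Run central permuted blocks in the IRT within the four duration-by-TFI strata, at about 140/4 = 35 subjects each. If site balance is wanted, use minimization with a random element on the three margins (site, duration, TFI) instead of crossing them.

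Make conforming edits in the synopsis (Study Design and Methods), Section 3 and Section 5.2.3. Also align the site terms in Sections 11.4.2.1, 11.4.2.2.2 and 11.4.2.2.3 with the new scheme; the synopsis version of the primary test already omits site. These should change together. For two subjects in the same site cell, the chance of opposite arms is (b/2)/(b − 1), which is 1, 2/3 or 3/5 for blocks of 2, 4 or 6. Without site blocks it is about 1/2. An analysis still crossed with site would therefore have slightly fewer informative cells than now.

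The cost is an IRT specification change and edits to those sections. The downside is that balance within a site is no longer forced, though the present scheme barely provides it at about 2.5 subjects per site. Kit resupply must also allow for unequal arms at a site.
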